The SWOG SDMC will provide a list of patients and time points to the Bank for distribution to the Natera laboratory. For each patient, an H&E slide from the primary tumor or lymph node metastasis will be scanned to a 40X digital image for digital pathology review by [name], who will provide specimen quality data (e.g., %tumor vs. necrosis, %tumor vs. normal, confirmation of concordance with institutional diagnosis, and comments when applicable) and will digitally annotate slides, as needed, for specimens that will require macrodissection to enrich tumor content. Following pathology QA review, the Bank will either scrape unstained slides (macrodissected as needed), or section FFPE blocks. All tissue will undergo co-extraction for DNA and RNA.

DNA will be extracted from buffy coat from one time point for each patient.

All nucleic acids will undergo quantitation and QC before storage in a -80°C freezer.

For each patient, the Bank will ship the following specimens to Natera on dry ice for overnight delivery:

- At least 500 ng DNA from primary tumor or lymph node metastasis and DNA from buffy coat
- A minimum of 4 ml of frozen plasma from Baseline
- A minimum of 4 ml of frozen plasma at start of cycle 3
- A minimum of 4 ml of frozen plasma at start of cycle 4
- A minimum of 4 ml of frozen plasma at removal from protocol therapy or relapse

18.10 Translational Medicine: Association of Circulating Tumor DNA (ctDNA) with Relapse-Free Survival in High-Risk, Resected Melanoma Patients

a. Objectives

1. Primary (integrated): To evaluate associations between pretreatment ctDNA (present versus absent) and relapse within 2 years of randomization in a case-control analysis across treatment arms
2. Secondary (integrated): To evaluate associations between pretreatment ctDNA and relapse within 2 years of randomization in a case-control

analysis within each treatment arm (after treatment arm data are unblinded to investigators).

3. Secondary (integrated): To evaluate associations between “early-on treatment” ctDNA levels and relapse within 2 years of randomization
4. Secondary (integrated): To describe ctDNA levels at end of therapy and time of relapse

b. Background

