From a double-blind, randomized, placebo-controlled trial, Eggermont, AMM et al. reported improved relapse free survival with adjuvant pembrolizumab in high risk, resected, Stage III melanoma patients compared to placebo. Specifically, pembrolizumab therapy was associated with a one-year rate of recurrence-free survival of 75.4% [95% confidence interval CI, 71.3 to 78.9] vs. 61.0% [95% CI, 56.5 to 65.1] in the placebo cohort. Thus, while anti-PD-1 therapy reduces the risk of disease progression of Stage III melanoma, 25% of patients are predicted to relapse within 1-year. For those untreated, up to 39% will relapse. At present, there are no biomarkers available to predict which of these patients are most likely to relapse. Improving outcomes for these patients in the future will require significant advancements in risk stratification tools.

The Signatera test, offered by Natera, is an emerging biomarker that has shown promising clinical utility for the detection of minimal residual disease and early detection of relapse. (1, 2, 3, 4) The assay quantifies cell free, circulating tumor DNA (ctDNA) present in plasma, down to a 0.1% mutant allele fraction. In patients with non-small cell lung cancer, colorectal cancer, muscle-invasive bladder cancer and breast cancer, studies with Signatera have shown an unprecedented positive predictive value (PPV) for relapse ranging from 93%-100% with an average lead time of 2.8-9.5 months compared to radiographic detection. (5, 6, 7, 8)

The **S1404** Stage III melanoma cohort includes post-operative plasma samples collected prior to the initiation of immunotherapy. With these samples, we may be able to discern if baseline ctDNA levels can risk stratify patients. The overall goal is to determine if highly sensitive, tumor-guided ctDNA testing can distinguish **S1404** patients who remain disease free from those who have relapsed. We hypothesize that the Signatera test results will be associated with relapse outcomes in the trial (and within each treatment arm) and that nondetectable ctDNA levels will be associated with lack of relapse within 2 years. For patients who have detectable ctDNA at time zero, we hypothesize that reduction in ctDNA levels will be associated with a lack of relapse within 2 years.

c. Experimental Research Technique

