With 100 total patients, 50 cases and 50 controls, and assuming 24% of control patients (no relapse or death within first two years) have detectable baseline ctDNA levels, we will have 90% power with a two-sided alpha of 5% to detect an odds ratio (OR) of 5.3 or more extreme if the correlation between cases and controls is 0.5. If the correlation is lower than 0.5, we have additional power. For example, if the correlation is 0.2, we have 90% power to detect an OR of 4.26 or more extreme.

For secondary analyses we will:

- evaluate baseline ctDNA as a quantitative covariate in a conditional logistic regression model,
- evaluate associations between presence/absence of ctDNA and quantitative ctDNA levels at the third and fifth cycles and relapse within 2 years using conditional logistic regression and landmark analyses,
- descriptively summarize changes in ctDNA levels over time using descriptive statistics including means, medians, and inter-quartile ranges and spaghetti plots
- perform all the above analyses within each treatment arm, and fit regression models with a treatment arm interaction covariate (to be performed after results by treatment arm from the trial are released by the DSMC).

No information on arm label will be provided during the processing, labeling, or analyses of this project until the DSMC releases results of the trial.

Analyses and interpretation of data are planned to be completed within 1 year of the receipt of specimens.

e. Data Analysis

Natera will report ctDNA levels to SWOG Statisticians. SWOG statisticians will perform all analyses linking ctDNA results with patient-level data.

f. Specimen Information

Exome sequencing and ctDNA detection will be performed by Natera and statistical testing will be performed by SWOG statisticians ctDNA and outcome correlation data will be reported to [name] (PI).

The SWOG Biospecimen Bank - Lab #201 will ship the following specimens to Natera on dry ice for overnight delivery as outlined in Section 18.9.c:

- 1) DNA from FFPE tumor
- 2) DNA from germline (buffy coat)
- 3) frozen plasma aliquots

Natera
[name]

Natera study contact:
[name], MBA (Medical Director, Oncology)
[contact]
[contact]

Specimens used:

Eligible patients who received ipilimumab or pembrolizumab on **S1404**. This proposal requires:

- primary tumor or lymph node metastasis AND plasma AND buffy coat from baseline,

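### Section 18.10b hypothesises that a fall in ctDNA among baseline-detectable patients predicts freedom from relapse, but no inferential analysis in 18.10d tests it or separates on-treatment ctDNA from the baseline association.

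*Combined protocol and SAP*

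**What the plan says.** The hypothesis is in the background of the ctDNA appendix, Section 18.10b: "For patients who have detectable ctDNA at time zero, we hypothesize that reduction in ctDNA levels will be associated with a lack of relapse" over a 2-year horizon. It concerns one subgroup (detectable at baseline) and one quantity (change).

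The listed secondary objective (18.10a, item 3, repeated in 1.4 item f) is different. It asks for the association between early on-treatment "ctDNA levels and relapse within 2 years of randomization".

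The secondary analyses in 18.10d are four bullets:

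- Baseline ctDNA is modelled as a quantitative predictor on its own.
- The on-treatment bullet is to "evaluate associations between presence/absence of ctDNA and quantitative ctDNA levels at the third and fifth cycles and relapse within 2 years using" matched-pair (conditional) logistic models and landmark methods. No covariate is named, and there is no restriction to baseline-detectable patients.
- The change bullet is to "descriptively summarize changes in ctDNA levels over time using descriptive statistics" and plots. No model links change to relapse.
- All of these are repeated by arm, with an arm interaction, once the DSMC has released results.

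Cases and controls are matched on stage group and PD-L1 status, so pairing does not balance baseline ctDNA either.

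**The concern.** An undetectable result at the later draw covers two kinds of patient: those whose ctDNA cleared on treatment and those who never had detectable ctDNA. The reduction hypothesis concerns only the first kind, but the planned model treats them alike. If baseline ctDNA predicts relapse and detectability persists to some degree, the later result will be associated with relapse even when change on treatment carries no information.

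Section 18.10c presents the assay as serial testing for monitoring. Whether a repeat test adds to the baseline test is therefore a natural question for readers, and the plan has no model that answers it. A model chosen after the data are seen would be post hoc.

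**Working it through.** **1. Inputs from 18.10d.** There are 50 cases and 50 controls, with 24% of controls detectable at baseline. The plan claims 90% power at two-sided 5% "to detect an odds ratio (OR) of 5.3 or more extreme if the correlation between cases and controls is 0.5"; and "if the correlation is 0.2, we have 90% power to detect an OR of 4.26 or more extreme".

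**2. Reproducing the plan's figure.** The standard matched case-control power formula (Dupont; one control per case, 50 pairs) gives 89.9% for odds ratio (OR) 5.3 with correlation 0.5, and 89.7% for OR 4.26 with correlation 0.2. The stated power holds up under that formula, but it covers the baseline analysis only. No power is stated for the on-treatment or change analyses.

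**3. Baseline positivity in cases.** At OR 5.3: 5.3 × 0.24 / (1 + 4.3 × 0.24) = 1.272 / 2.032 = 0.626. Expected baseline-detectable patients are 50 × 0.626 ≈ 31 cases and 50 × 0.24 = 12 controls.

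**4. Pairs left at Week 13.** The start of cycle 3 is used because the analysis text and the specimen list both include it. Under the RFS models in 11.3, the share of 2-year events falling before that visit is (1 − exp(−λt)) / (1 − exp(−2λ)).

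- λ = 0.67 (control): 19% at 12 weeks, 21% at 13 weeks.
- λ = 0.48 (pembrolizumab): 17% at 12 weeks, 18% at 13 weeks.

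Taking 18% of 50 removes 9 cases and leaves 41 pairs.

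**5. What the unadjusted model would show if change were uninformative.** Let relapse depend on baseline ctDNA only, with clearance c and new conversion v the same in cases and controls. Both rates are assumptions. For baseline positivity p, on-treatment positivity is p(1 − c) + (1 − p)v.

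- c = 30%, v = 2%: cases 0.626 × 0.70 + 0.374 × 0.02 = 0.446; controls 0.24 × 0.70 + 0.76 × 0.02 = 0.183.
- c = 90%, v = 5%: cases 0.626 × 0.10 + 0.374 × 0.05 = 0.081; controls 0.24 × 0.10 + 0.76 × 0.05 = 0.062.

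| Clearance | Conversion | Cases + | Controls + | On-treatment OR | Share of baseline log-OR | Significant, 41 pairs |
|---|---|---|---|---|---|---|
| 30% | 2% | 0.446 | 0.183 | 3.6 | 77% | 74% |
| 70% | 5% | 0.206 | 0.110 | 2.1 | 45% | 20% |
| 90% | 2% | 0.070 | 0.039 | 1.8 | 37% | 8% |
| 90% | 5% | 0.081 | 0.062 | 1.3 | 17% | 6% |

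The share is ln(on-treatment OR) / ln(5.3). The last column is a McNemar score test at two-sided 5% with independent pairs.

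**6. With baseline in the model.** By construction the true baseline-adjusted on-treatment OR is 1. In simulations of about 600 data sets per setting (unmatched logistic regression, 41 against 41, clearance 30-70%, conversion 5%), the on-treatment term was significant about 5% to 8% of the time. Without baseline it was significant about 19% to 69% of the time.

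**7. Who is being compared.** Among on-treatment-negative controls, the fraction never positive is 0.76(1 − v) / (1 − controls +). At 30% clearance and 2% conversion this is 0.745 / 0.817 = 91%. At 70% and 5% it is 0.722 / 0.890 = 81%.

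**8. What a direct test can support.** With independent pairs, both members are baseline-detectable in 50 × 0.24 × 0.626 ≈ 7.5 pairs, too few for conditioning on pairs. Removing 18% of the cases for early relapse leaves 31.3 × 0.82 ≈ 26. Fisher's exact test on 12 controls and 26 cases has about 34% power for 70% versus 40% clearance, and about 57% for 70% versus 30%.

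**The case against.** The strongest reply is that the on-treatment model matches its objective. Items 18.10a(3) and 1.4(f) ask about early on-treatment levels and relapse. Whether a Week 13 test identifies patients who will relapse is a legitimate prognostic question, and for that question cleared and never detectable are the same result. No listed objective claims incremental value over baseline, and the reduction sentence stands only in the background. All of this stands, and it is why the unadjusted model should stay.

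Three stronger readings are tempting, and the documents support none of them:

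- **The on-treatment analysis largely repeats the baseline one.** That depends on how far detectability persists, which the documents do not give. Under the assumptions above, the inherited share runs from about 17% to 77% of the baseline log-OR.
- **A significant on-treatment result is to be expected even if change is uninformative.** Over much of the range a non-significant result is more likely.
- **The plan would present the level model as confirming the reduction hypothesis.** Nothing in 18.10d says so. The plan is silent on adjustment and does not rule it out.

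The illustration also pairs OR 5.3 with independent pairs, whereas the plan ties 5.3 to a correlation of 0.5. At zero correlation, the formula that reproduces the plan's power gives a detectable OR of about 3.8. The rejection range for 30-70% clearance is then 14% to 55%, instead of 20% to 74%.

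Finally, with about 12 baseline-detectable controls, merely describing change is defensible. This limits what the added analysis can show, but does not supply a test of the stated hypothesis.

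**Conclusion.** The gap is real and narrow. The hypothesis in 18.10b has no matching inferential analysis in 18.10d, and the planned on-treatment model cannot separate on-treatment information from the baseline association. That follows from the text and needs no assumption about persistence.

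The size does need assumptions. With relapse depending on baseline ctDNA alone (OR 5.3, independent pairs, 41 pairs at Week 13), clearance of 30-90% and conversion of 2-5%, the unadjusted OR would be about 1.3 to 3.6, and significance would be reached about 6% to 74% of the time. A positive result could therefore not be credited to on-treatment ctDNA, and how misleading it would be is unknown. This is a secondary analysis in a 100-patient banked-sample appendix and does not touch the trial's primary endpoints or alpha.

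**What to change.** In 18.10d:

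1. Keep the unadjusted on-treatment model, and add the same model with baseline ctDNA (present/absent, or log level) as a covariate.
2. Prespecify, labelled exploratory, an analysis restricted to baseline-detectable patients that relates clearance (yes/no) or log change from baseline to relapse within 2 years. Use an unconditional exact or penalised logistic model with at most stage group as a covariate. About 12 controls cannot support clearance plus arm, stage group and three-level PD-L1.
3. Add arm only after the DSMC has released results, in line with the existing rule in 18.10d that withholds arm labels.

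The cost is a few sentences. Baseline plasma is already required for every selected patient (18.9c, 18.10f), so no new samples or assays are needed. The downside is wide intervals and low power in the baseline-detectable subset (about 12 controls and 31 cases before early relapses).
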